The effect of the three exercise interventions on muscle tissue oxygenation will be determined from baseline and at 12 week and 24 week follow-up by measuring limb oxygenation of the quadricep (during leg extensions) and tibialis anterior muscle (during treadmill testing) of all study groups as quantitated by non-invasive infrared spectroscopy using an InSpectra™ Tissue Spectrometer.

Exercise-facilitated recovery of peripheral nerve function in previous subjects is postulated to have occurred due to a decrease in tissue hypoxia. We will directly test this thesis by quantitating tissue oxygenation of our subject population by measuring muscle tissue oxygenation levels. In our hands, the InSpectra™ Tissue Spectrometer successfully quantitated tissue oxygenation from pre-exercise ( $StO_2 = 92\%$ ), to peak exercise ( $StO_2 = 49\%$ ), and recovery ( $StO_2 = 91\%$ ). Interestingly, in some subjects  $StO_2$  levels at peak of exercise are non-responsive and remain at baseline saturation (>90%). These subjects may be experiencing indolent autonomic neuropathy. Conversely, other subjects peak  $StO_2$  levels drop below 5% saturation, possibly reflecting previously undetected large vessel disease.

**Muscle tissue oxygenation** (oxygen saturation of hemoglobin;  $\%StO_2$ ) and aerobic power ( $VO_2 \text{ mL kg}^{-1} \text{ min}^{-1}$ ) will be measured in the quadricep (during leg extensions) and the tibialis anterior (during walking) muscle groups of all subjects using near infrared spectroscopy (InSpectra™ Tissue Spectrometer, Hutchinson Technology, Hutchinson, MN). These studies will be performed throughout each incremental symptom-limited treadmill test. The InSpectra™ Tissue Spectrometer is a non-invasive monitoring system that measures an approximated value of percent hemoglobin oxidation in tissue ( $\%StO_2$ ) based on spectrophotometric principles. The spectrometer measures tissue absorbance values at wavelengths between 650-900 nanometers. The volume of tissue measured by the InSpectra™ Tissue Spectrometer is directly related to the distance between the illumination and the detection fibers. The sensor probe will be placed on the quadricep or the anterior tibialis muscle of the same limb used for determining peripheral nerve function. This product is routinely used by this laboratory and has proven to be a reliable measure of  $StO_2$ . The spectrometer successfully tracks minute-by-minute tissue oxygenation from pre-exercise, to peak exercise, and recovery.  $StO_2$  measures will be taken before, during and post exercise until measures approach the pre exercise values.

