
**Stopping Intervention & Intent-to-Treat Principle:** Subjects are carefully screened at the start of the study in an effort to minimize the need for medical withdrawal. As noted above, the subject's primary care physician is kept informed throughout the study, and if it is the primary care physician's judgment that the subject should not continue in the study, the subject is withdrawn. We have withdrawn patients in the past for worsening joint arthritis, new cancer diagnosis necessitating treatment, diagnosis of coronary artery disease at the mid-testing period (as patients become capable of more work, previously undiagnosed coronary artery disease may surface), or unexpected injuries (e.g., car accidents). If a subject is unable to complete the full intervention protocol, the last available electrodiagnostic primary outcome measurement will be used for the analysis. In these cases, the primary analyses will be based on intention-to-treat principles (i.e., all randomized subjects will be included in the analyses). Protocol adherence will be treated as a co-variate to control for subject compliance. The primary analyses will be repeated, restricted to subjects who complete the intervention protocol. Analysis of covariance (see above) will be used to compare the responses between the intervention groups. Regression will then be used to determine whether the observed intervention persists using adjustment for baseline covariates and measures of treatment compliance.

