**Exercise Interventions:** Aerobic exercise will consist of treadmill walking. Isokinetic strength promoting leg extensions will be performed on a calibrated Biodex System 3 dynamometer. The use of Biodex machine is proposed as an experimental means of determining the impact isokinetic strength training has on recovery of peripheral nerve function in diabetic neuropathic veteran. Demonstrating effect with isokinetic strength training, or in combination with aerobic training, will be used as a strong rationale for implementing interventions of this type into clinical rehabilitative practice. **Subjects randomized to the combined aerobic plus isokinetic strength training** will receive isokinetic strength training followed by aerobic treadmill training so that maximal benefits can be gained from the strength program. Patients will be allowed to rest 15-30 minutes between strength and aerobic training with each session ending with a 10 minute cool-down period. Based on prior experience with exercise intervention studies, we anticipate an 80% retention rate within this intervention group. Our sample size for this group includes a 20% attrition rate to compensate for subjects unable or unwilling to complete the 24-week intervention program. Sustainability of interventions will be evaluated by repeated testing at 24 weeks. **All subject groups will participate in identical biweekly diabetes-related Health Promotion Educational seminars designed to normalize participation.**

Subjects randomized to aerobic, isokinetic, or the combination of aerobic plus isokinetic exercise group will be trained in the Physical Performance Laboratory three times weekly. A 10 minute warm-up consisting of stretching

and flexibility exercises will precede all training sessions. Exercised training duration and intensity will progress as listed in the following table:

Strength Training (maximal isokinetic muscle action; velocity of $90^{\circ} \cdot s^{-1}$ )		Aerobic Training (Walking)
Weeks 1-2	3 sets, 10 repetitions, 1 min rest between sets	25 min at 60-70% $VO_2$ peak; 5 min 71-80% $VO_2$ peak
Weeks 3-4	4 sets, 10 repetitions, 1 min rest between sets	25 min at 60-70% $VO_2$ peak; 10 min 71-80% $VO_2$ peak
Weeks 5-6	5 sets, 10 repetitions, 1 min rest between sets	25 min at 60-70% $VO_2$ peak; 15 min 71-80% $VO_2$ peak
Weeks 7-8	6 sets, 10 repetitions, 1 min rest between sets	25 min at 60-70% $VO_2$ peak; 17 min 71-80% $VO_2$ peak; 3 min 81-90% $VO_2$ peak

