**Conventional Care (Health Promotion Education) Intervention:** The conventional care and Health Promotion Education intervention will consist of 12 clinical visits over 24 weeks. The clinical nurse coordinator ([name], R.N.) will conduct the educational clinical visits. During these visits, subjects' blood glucose for the previous two weeks will be retrieved from home glucometers. Their current blood sugar will be checked with POC glucometer and vital signs at rest determined. **ALL subjects will participate in a series** of twelve 45-minute skill building sessions. Initial assessments of personal lifestyle habits will be completed. These include nutrition (logs of food intake, nutritional value, shopping patterns, cooking/restaurant habits and food budget), body hygiene, especially foot care and podiatry needs) and consultations needs. Food lab 'hands-on' preparation sessions will be conducted. Classes will also incorporate the importance of medication management, blood sugar monitoring, graphing patients glycated hemoglobin values over time and the interaction of these with food/fluid intake and daily activities. Patients will also access the internet and obtain current best source information on Diabetes and other topics of interest. The clinic/educational visits should not affect the patients' neuropathies. The non-exercised control intervention group receiving conventional care will be compared with the exercised intervention groups receiving conventional care plus strength, aerobic, or combined training. Actical accelerometers will be used on all study participants to monitor variations that might occur in the exercised patterns of the control subjects, and any change in fitness will be assessed by peak oxygen uptake and exercise tolerance during the incremental treadmill exercise tests performed at 12 & 24 weeks.

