### **Statistical Analysis Plan**

In response to reviewer's concerns, we addressed statistical concerns with this program by recruiting the services of [name]. (Associate Professor of Preventative Medicine and Epidemiology and biostatistician, Loyola University Chicago). [name] has generously agreed to serve as lead statistician of this study. He will be responsible for the statistical analyses of all collected study data. The statistical analytical sections of this revised application, including determination of subject sample size, have been substantially revised per the advice of [name].

All data will be entered in SPSS 15 for Windows (SPSS, Inc., Chicago, IL). Results will be expressed as mean  $\pm$  SEM of (n) observations. To directly test the hypothesis that a combined influence of aerobic and isokinetic strength training will enhance recovery of peripheral nerve function, measures of conduction velocity and amplitude will be analyzed by way of a 2 x 2 factorial analysis of covariance followed by a Bonferroni's multiple comparison post-hoc analysis according to the following scheme:

		Isokinetic Strength Training	
		No	Yes
Aerobic Training	No	Sedentary controls	Isokinetic strength exercise
	Yes	Aerobic exercise	Aerobic plus isokinetic strength exercise

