Data collected at 12 weeks will be analyzed, using baseline measurements as a covariate. This will be repeated with the data that are collected at 24 weeks. In both analyses, primary interest will be in the combined aerobic training plus isokinetic strength training interaction. We hypothesize that patients with the combined exercise program will experience the best outcome. Although data will be collected across three time periods (baseline, 12 weeks, and 24 weeks), we have chosen to not employ a repeated measures design. There are two reasons for this: (i) the proposed study is designed to determine the combined influence of aerobic and isokinetic training on recovery of peripheral nerve function, which we believe is best achieved with a factorial design and (ii) our previous experience identified baseline differences among groups of diabetic neuropathy subjects. These group differences will go uncontrolled using a repeated measures design, but can be controlled statistically with analysis of covariance. Therefore, the aerobic plus isokinetic strength training interaction for our primary electrodiagnostic measures will be observed at 12 weeks, controlling for baseline values. This will be done again for the data collected at 24 weeks. A 2 x 2 factorial analysis of covariance also will be conducted with secondary outcome measures such as changes in aerobic capacity, peak torque, pain perception and health care use. Again, data collected both at 12 and 24 weeks will be analyzed using baseline measurements as a covariate. These analyses will allow us to observe the extent to which the secondary measures dovetail with the primary electrodiagnostic measures. In addition, primary outcomes will be correlated with secondary outcomes in order to assess the association of recovery of peripheral nerve function and quality of life. Partial correlation coefficients will be computed at 12 weeks, controlling for baseline values. This will be repeated for the data collected at 24 weeks.

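### The intention-to-treat section adds an undefined, post-randomisation adherence covariate to a primary model that the Statistical Analysis Plan adjusts for baseline alone

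*Combined protocol and SAP*

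**What the plan says.** Two places describe the analysis of the primary electrodiagnostic measures.

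- **Statistical Analysis Plan.** Conduction velocity and amplitude are to be "analyzed by way of a 2 x 2 factorial analysis of covariance". The covariate is then named: "Data collected at 12 weeks will be analyzed, using baseline measurements as a covariate". The same is done at 24 weeks, and primary interest is placed on the aerobic-by-strength interaction. Baseline is the only covariate named, although the text does not say in so many words that there is no other.
- **Stopping Intervention & Intent-to-Treat Principle.** Here "the primary analyses will be based on intention-to-treat principles (i.e., all randomized subjects will be included in the analyses"). The next sentence is "Protocol adherence will be treated as a co-variate to control for subject compliance". The one after it repeats the primary analyses in completers. The paragraph closes: "Regression will then be used to determine whether the observed intervention persists using adjustment for baseline covariates and measures of treatment compliance".

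No section gives a measure of adherence, a scale, a time window or a value for the control arm. Under Exercise Interventions, subjects in the exercise arms "will be trained in the Physical Performance Laboratory three times weekly". Under Conventional Care, all subjects, controls included, have "twelve 45-minute skill building sessions". The time window is unclear too: the exercise programme is described as 12 weeks in the objectives, while Exercise Interventions also speaks of a 24-week intervention programme.

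**The concern.** The adherence sentence stands between the intention-to-treat statement and the completer repeat of the primary analyses. Its natural reading puts adherence in the primary model. An analyst working from that paragraph and one working from the Statistical Analysis Plan would fit different models, and each could claim to follow the plan. Evaluation takes place after the code is broken, so the choice could be made with results in view.

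The two models also estimate different things. Randomisation balances what precedes it, and adherence follows it. The protocol's own list of past withdrawals (worsening arthritis, new cancer, coronary disease surfacing as work capacity rises) shows that stopping can depend on health and on what the arm asks of the subject. Health may also affect nerve function. Adjusting for such a variable can remove part of a real effect and can create an effect where there is none.

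The closing regression raises the same difficulty in a milder form. It is given the task of testing whether the effect holds up after compliance adjustment, and nothing says that it cannot qualify the randomised result.

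**Working it through.** **Reproducing the plan's figures.** For a 1-df interaction in four equal cells, the noncentrality is N x f². Velocity, f = 0.36: 16 per group gives 80.9% power and the plan's 17 gives 83.2%, so its figure reproduces, slightly on the safe side. At 25 per group power is 94.6%. Amplitude, f = 0.25: power at 25 per group is 69.7%. Enrolment: 20/(1 - 4/21) = 24.7, that is 25 per group. Dropping or adding a covariate changes the error degrees of freedom by one and leaves these sample sizes unchanged.

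**Implied SDs.** The preliminary-data table is not in the text, so the SDs are solved from SD = (interaction contrast/4)/f.
- Velocity: (43 - 39) - (39 - 38) = 3 m/s, so (3/4)/0.36 = 2.08 m/s.
- Amplitude: (4 - 2.4) - (1.9 - 1.9) = 1.6 mV, so (1.6/4)/0.25 = 1.6 mV.

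**What the adjustment does.** Leaving the baseline term aside, least squares gives

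adjusted contrast = unadjusted contrast - b x (same contrast of the arms' mean adherence),

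where b is the pooled within-arm slope of outcome on adherence. Its variance is SD² x [c/25 + (adherence contrast)²/W], where c is 4 for the interaction and 2 for combined minus control, and W is the within-arm sum of squares of adherence.

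**Case 1: exercise sessions only.** Assume control 0, other arms mean 0.8, within-arm SD s from 0.10 to 0.20. The interaction contrast of mean adherence is 0.8 - 0.8 - 0.8 + 0 = -0.8, and W = 3 x 24 x s² = 72s².

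- *Precision.* Without adherence, SE = 2.08 x √(4/25) = 0.83 m/s. With it, s = 0.10 gives 2.08 x √(0.16 + 0.64/0.72) = 2.13, and s = 0.20 gives 2.08 x √(0.16 + 0.64/2.88) = 1.29. Simulation (3,000 trials per scenario) with adherence kept between 0 and 1, which shrinks the effective SD, gives 1.40-2.19. Velocity interaction power falls from about 94% to 29-58% (27-57% on repeat). Amplitude SE rises from 0.64 to 1.08-1.69 mV and power falls from about 69% to 15-33%. Velocity combined minus control is still detected in 65-97% of trials.
- *Benefit proportional to dose.* The planned effects of 1, 1 and 5 m/s at mean adherence 0.8 give slopes of 1.25, 1.25 and 6.25, so b = 8.75/3 = 2.92. Combined minus control becomes 5 - 2.92 x 0.8 = 2.7 m/s. The interaction becomes 3 + 2.92 x 0.8 = 5.3 m/s. Simulation agrees (2.6-2.7 and 5.3).
- *No true effect, confounded adherence.* Assume adherence correlates 0.4 with a trait worth 0.5 SD of outcome. Then b = 0.4 x 0.5 x 2.08/s = 0.417/s, and the false interaction is 0.8 x 0.417/s = 3.3 m/s at s = 0.10 and 1.7 m/s at s = 0.20. The interaction test rejects in 26-34% of simulated trials (26-35% on repeat), not 5%.

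**Case 2: share of the assigned protocol completed, scored in every arm.** Velocity, same confounding, no true effect. Means are in the order control/strength/aerobic/combined.

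| Mean adherence | Combined - control: size of bias (m/s), rejection | Interaction: rejection |
|---|---|---|
| equal, 0.85 | none, 4-6% | 4-6% |
| 0.90/0.85/0.85/0.80 | 0.2-0.4, 7-10% | 4-6% |
| 0.95/0.85/0.85/0.65 | 0.6-1.3, 14-30% | 6-8% |
| 0.95/0.80/0.80/0.80 | 0.3-0.6, 7-16% | 5-10% (bias -0.25 to -0.63) |

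The formula agrees. In the third row, for example, the combined-minus-control adherence contrast is 0.65 - 0.95 = -0.30, so the bias is 0.30 x 0.417/s, or 1.25 at s = 0.10 and 0.63 at s = 0.20. The interaction SE rises at most from 0.84 (simulated) to 0.90.

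**Second check under different assumptions.** This used 4,000 trials, a health factor driving adherence (logit slope 1.0) and outcome (0.4 SD), and somewhat lower adherence in the combined arm. With no true effect, baseline-only ANCOVA rejected the interaction in 4.8-5.5% of trials. Adding adherence gave 90% with controls scored 0, 17% with controls scored 1, and 8% with controls scored on seminar attendance. The mean false interactions were +3.5, -0.6 and +0.3 m/s.

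**The case against.** The best defence is that the paragraph sets out a sequence: ANCOVA compares the groups, and a regression with compliance terms then follows. On that reading the adherence sentence merely anticipates the later regression, and the detailed Statistical Analysis Plan, which never mentions adherence, governs. This reading is possible, but it makes the adherence sentence redundant, since the regression is announced separately, and it ignores where the sentence sits. Nothing elsewhere settles the matter, so the text has to be reconciled on either reading.

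The second objection is that the largest figures need controls scored as zero, which the plan does not say. An all-arm score is at least as natural, since every subject has seminars to attend. Under such scores the harm to the interaction is mild (4-10% rejection), and the larger errors fall on combined versus control and need markedly unequal adherence. This stands as a limit on the size of the problem. It does not make the model right: whether the result is valid would turn on a definition that the plan does not contain.

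The third is that adherence distributions and confounding strength are assumed, SDs are back-calculated, and the simulations leave out dropout and the last-observation rule. That also stands. The figures are illustrative, not predictions. Finally, the wording that the regression comes afterwards does place it second, so its missing label is the lesser part of the point.

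**Conclusion.** The concern holds. As written, the intention-to-treat paragraph conditions the primary comparison on a variable that arises after randomisation, and it conflicts with the baseline-adjusted ANCOVA in the Statistical Analysis Plan. The adherence-adjusted contrast is not the effect of assignment. That conclusion rests on the design, not on the simulations.

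The size depends on the missing definition. It runs from no distortion (all arms scored, equal means) to loss of most of the precision of the interaction and a roughly one-in-three false-positive rate under the main assumptions with controls scored zero. A stronger set of assumptions took that rate to 90%. Because the primary model and the effect of primary interest are involved, this should be corrected before any outcome data are analysed.

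**What to change.** 1. Delete the adherence sentence from the intention-to-treat paragraph, so that the primary model there matches the Statistical Analysis Plan: the two factors, their interaction and the baseline value of the outcome. State in both places that there are no other covariates.
2. Define adherence: numerator, denominator, time window, and how control subjects are scored. Reconcile the 12-week and 24-week descriptions of the programme that bear on the denominator.
3. Label the compliance regression supplementary and observational, for example a dose-response analysis within the three exercise arms. State that it neither qualifies nor overrides the intention-to-treat result.

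The cost is one deleted sentence, one definition and one relabelled analysis. The sample size does not change. No new data are needed, because heart rate and blood pressure are already recorded at each training session, so attendance can be counted from existing records.
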